8.2 Participant demographics/other baseline characteristics

Country-specific regulations should be considered for the collection of demographic and baseline characteristics in alignment with CRF.

Participants demographic: full date (only if required and permitted) or year of birth or age, sex, race/predominant ethnicity (if permitted) and baseline characteristic data will be collected on all participants. Participant race/ethnicity are collected and analyzed to identify variations in safety and/or efficacy due to these factors as well as to assess the diversity of the study population as required by Health Authorities.

Relevant medical history/current medical conditions will include: date for diagnosis of PNH (and age for diagnosis and disease duration will be derived up to the date of screening), vaccination history, and MAVE history (dates and type). In addition, the number of transfusions and unit numbers of packed-RBC will be collected for the 12 months preceding Screening. For participants in China, historical data on hemoglobin, LDH and absolute reticulocyte count (ARC) laboratory values will be retrospectively collected for the 6 months preceding Screening.

Relevant medical history, smoking and alcohol history will also be collected.

Prior concomitant medications (including vitamins, herbal preparations, over the counter medications, and those medications highlighted in the entry criteria) **and procedures** (any therapeutic intervention including surgery, biopsies, or non-pharmacological therapy) taken prior to Screening will be recorded in the CRFs. Medications for the treatment of PNH preceding screening will be collected in the CRF.

Investigators have the discretion to record abnormal test findings on the medical history eCRF, if in their judgment, the test abnormality occurred prior to the informed consent signature.

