3. Its duration (start and end dates) or if the event is ongoing, an outcome of not recovered/not resolved must be reported
4. Whether it constitutes a SAE (see [Section 10.1.2](#) for definition of SAE) and which seriousness criteria have been met
5. Action taken regarding study treatment.

All adverse events must be treated appropriately. Treatment may include one or more of the following:

- Dose not changed
 - Dose Reduced/increased
 - Drug interrupted/withdrawn
6. Its outcome

Conditions that were already present at the time of informed consent should be recorded in medical history of the participant.

Adverse events (including lab abnormalities that constitute AEs) should be described using a diagnosis whenever possible, rather than individual underlying signs and symptoms.

Adverse event monitoring should be continued at least until 7 days after the last dose of study medication, or until the first day of dosing in the REP.

Once an adverse event is detected, it must be followed until its resolution or until it is judged to be permanent (e.g. continuing at the end of the study), and assessment must be made at each visit (or more frequently, if necessary) of any changes in severity, the suspected relationship to the interventions required to treat it, and the outcome.

Information about adverse drug reactions for the investigational drug can be found in the Investigator's Brochure (IB).

Abnormal laboratory values or test results constitute adverse events only if they fulfill at least one of the following criteria:

- they induce clinical signs or symptoms
- they are considered clinically significant
- they require therapy

Clinically significant abnormal laboratory values or test results must be identified through a review of values outside of normal ranges/clinically notable ranges, significant changes from baseline or the previous visit, or values which are considered to be non-typical in participant with the underlying disease. Alert ranges for laboratory and other test abnormalities are included in [Appendix 1](#).

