For selected laboratory parameters, abnormalities occurring at any time-point from scheduled, unscheduled and premature discontinuation visits considering all post-baseline on-treatment data will be summarized. Where normal ranges are available, abnormalities in laboratory data will be listed by participant and visit/time.

Liver toxicities

A criterion-based table for selected liver function tests and AEs will be presented including the number and percentage of the events described in [Table 2-2](#). In the PNH indication, aspartate aminotransferase (AST) can increase for reasons not related to liver toxicity and therefore should not be considered in the derivation of liver toxicities. Moreover INR is routinely monitored and can be used for the definition of liver function events. Events for the PNH indication are described in [Table 2-2](#).

Liver toxicity finding based on laboratory values and accounting for presence of bone pathology, symptoms, Gilbert syndrome will be presented. AEs collected in the analysis dataset and related

to liver toxicities (Jaundice, AE potentially indicative of a liver toxicity) will either be reported separately in a specific table or will simply be displayed as part of the general AE tables.

Table 2-2 Liver Toxicities

Definition	Label for output display
Potential Hy's Law case	
(ALT or AST > 3 × ULN) and TBL > 2 × ULN and ALP to ≤ 2 × ULN in the absence of bone pathology ^a (ALT or AST > 3 × ULN) and TBL > 2 × ULN and ALP to ≤ 3 × ULN in the presence of bone pathology ^a	Potential Hy's Law case
ALT elevations	
If ALT ≤ ULN at baseline: (ALT > 3 × ULN) and INR > 1.5 If ALT > ULN at baseline then criteria for ALT are defined as ALT > 2 x baseline or > 300 U/L and INR > 1.5	(ALT > 3 × ULN) and INR > 1.5
ALT > 8 × ULN	ALT > 8 × ULN
If ALT ≤ ULN at baseline: ALT > 5 to ≤ 8 × ULN If ALT > ULN at baseline then criteria for ALT are defined as ALT > 3 x baseline or > 300 U/L	ALT > 5 to ≤ 8 × ULN
If ALT ≤ ULN at baseline: ALT > 3 to ≤ 5 × ULN (accompanied by symptoms) ^a If ALT > ULN at baseline then criteria for ALT are defined as ALT > 2 x baseline or > 300 U/L (accompanied by symptoms) ^a	ALT > 3 to ≤ 5 × ULN with symptoms
If ALT ≤ ULN at baseline: ALT > 3 to ≤ 5 × ULN (patient is asymptomatic) ^a If ALT > ULN at baseline then criteria for ALT are defined as ALT > 2 x baseline or > 300 U/L (patient is asymptomatic) ^a	ALT > 3 to ≤ 5 × ULN no symptoms
ALP (isolated)	

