ALP > 2 × ULN (in the absence of known bone pathology) ^a ALP >3 x ULN (if bone pathology ^a is present)	ALP > 2 × ULN (>3 x ULN if bone pathology is present)
TBL: total bilirubin ALT: alanine aminotransferase ^a concomitance between abnormal laboratory values and symptoms or disease (bone disease, Gilbert syndrome) will be established based on reported AEs or medical history with a start date prior to laboratory measurement and stop date posterior to laboratory measurement. Selection of AEs and medical History is described in Table 2-3 and provided in eCRS ^b Selection of AEs described in Table 2-3 and provided in eCRS	

When a criterion contains multiple laboratory parameters (e.g. ALT or AST > 3 × ULN), the criterion should be considered as met only if the elevation in parameters occurs on the same sample day (as evidenced by the same date that the lab samples were taken).

Table 2-3 Definition of symptoms and AEs for liver toxicities

Term in table	MedDRA term(s)
Bone pathology	HLGT = Bone disorders (excl congenital and fractures)
Symptoms:	
Severe Fatigue ⁽¹⁾	PT = Fatigue
Abdominal pain right upper quadrant	PT = Abdominal pain upper
Nausea	PT = Nausea
Vomiting	PT = Vomiting
General malaise	PT = Malaise
Rash with eosinophilia	PT = Drug reaction with eosinophilia and systemic symptoms
Gilbert syndrome	PT = Gilbert's syndrome
Jaundice	PT = Jaundice PT = Jaundice cholestatic
AEs indicative of liver toxicity	
Hepatic failure	HLT = Hepatic failure and associated disorders
Hepatic fibrosis and cirrhosis	HLT = Hepatic fibrosis and cirrhosis PT = Hepatic cirrhosis
Non-infectious hepatitis	PT = Hepatitis PT = Hepatitis acute PT = Hepatitis toxic PT = Hepatitis fulminant PT = Hepatitis chronic active PT = Hepatitis chronic persistent
Liver neoplasm	HLGT = Hepatobiliary neoplasms

HLT: High Level Term

HLGT: High Level Group Term

MedDRA codes listed above are based on version 23.1 The list will be updated for each MedDRA version change and will be included in the eCRS. eCRS will be the reference for analyses.

(1) presence of Fatigue term with severity ≥ "Severe"

Renal alert values will be summarized where renal alert values are identified as:

- Serum creatinine increase ≥ 25% compared to baseline during normal hydration status
- New onset dipstick proteinuria ≥ 3+

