2.13 Interim analysis

No formal interim analyses of efficacy are planned in this study. A data cut-off will be applied and a clinical study report (CSR) will be produced for submission at the time the last patient has completed the core treatment period. An additional CSR will be produced when the last participant has completed the last visit in the extension treatment period, when the final study database has been locked. In addition, if deemed required (e.g. to support regulatory submissions to Health Authorities) interim safety analyses may be produced while the study is still ongoing. If there is an interim lock for safety analyses, [REDACTED]

[REDACTED] The interim report will not consider inferences based on efficacy.

Safety data will be monitored by an independent DMC, and analyses to the effect of this evaluation will be performed during the course of the study with the frequency to be determined in the DMC Charter. Access to a limited number of efficacy measurements by the DMC will be

provided solely for the purpose of evaluating benefit of treatment with iptacopan against any risk. The DMC will function under the the DMC Charter which has been finalized. The Charter includes guidelines for communication concerning safety of participants between the DMC and the sponsor representative to ensure that these are in keeping with the sensitive nature of the open label trial and do not introduce bias.

3 Sample size calculation

The sample size is calculated based on the half-width (the margin of error in the estimate) of a 2-sided 95% confidence interval for the proportion of participants reaching the status of responder (primary endpoint). The proposed sample size of 40 participants is sufficient to achieve a target absolute margin of error not larger than 0.155.

The different scenarios of observed response rate and its 95% confidence intervals are shown in [Table 3-1](#).

Table 3-1 Precision of response rate with N = 40

Sample Size	Observed Response Rate	Unadjusted 95% Confidence Interval
40	30%	(15.8%,44.2%)
40	40%	(24.8%,55.2%)
40	50%	(34.5%, 65.5%)
40	60%	(44.8%,75.2%)

The lower bound of the two-sided 95% confidence interval of the response rate obtained from the primary analysis will be compared to a threshold of 15% and exceeding the threshold is sufficient for demonstration that iptacopan improves hematological response in PNH patients with hemolysis and anemia in the absence of transfusions.

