5.1 Imputation rules

5.1.1 AE date imputation

5.1.1.1 AE end date imputation

Rules for imputing AE end dates are stated below. Date of last contact in the study has been defined as in [Section 2.1.1.5](#).

1. If the AE end date month is missing, the imputed end date should be set to the earliest of the (date of last contact, 31DECYYYY, date of death).
2. If the AE end date day is missing, the imputed end date should be set to the earliest of the (date of last contact, last day of the month, date of death).
3. If AE year is missing or AE is ongoing, the end date will not be imputed.

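### The liver-toxicity concomitance rule in SAP Table 2-2 needs a stop date after the sample, so records with no stop date at cut-off, or that start or end on the sample day, do not count as concomitant

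*SAP*

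**What the plan says.** SAP Section 2.7.3 presents a criterion-based liver table that is meant to take symptoms and bone pathology into account. Two parts of Table 2-2 depend on them:

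- **Symptom split.** One row is labelled "ALT > 3 to ≤ 5 × ULN with symptoms", and a companion row holds the same elevation without symptoms. Participants with raised baseline ALT have equivalent baseline-based criteria.
- **ALP limit.** In the potential Hy's Law row, the ALP ceiling is 2 × ULN without bone pathology. The version for bone pathology reads "and TBL > 2 × ULN and ALP to ≤ 3 × ULN in the presence of bone pathology". The isolated-ALP row starts above 2 × ULN, or above 3 × ULN if bone pathology is present.

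Footnote a defines concomitance from reported AEs or medical history "with a start date prior to laboratory measurement and stop date posterior to laboratory measurement". It then adds: "Selection of AEs and medical History is described in Table 2-3 and provided in eCRS".

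Three other places determine which records have a stop date:

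- SAP 5.1.1.1: "If AE year is missing or AE is ongoing, the end date will not be imputed".
- Protocol 10.1.1, on duration: "if the event is ongoing, an outcome of not recovered/not resolved must be reported".
- Protocol 8.2 introduces the data to be collected with "Relevant medical history/current medical conditions will include", so conditions still present at entry are recorded as history. SAP 5.1 has date rules for AEs and concomitant medications but none for medical history.

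On timing, SAP 2.13 says: "A data cut-off will be applied and a clinical study report (CSR) will be produced for submission". SAP Section 1 confirms that this report includes extension-period safety data collected up to the cut-off.

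**The concern.** A concomitance rule should ask whether the condition was present when the sample was taken. Footnote a asks for something narrower: a start before the sample and a recorded stop after it. A chronic bone disorder in medical history may have no stop date. A symptom unresolved at the cut-off has none either. A symptom that first appears on the day of an unscheduled sample has a start date equal to the sample date, not before it.

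If such records fail, a symptomatic ALT elevation can be tabulated as asymptomatic, although protocol Table 16-1 treats the two states as different triggers. A participant with bone disease can also be tested against the wrong ALP limit. That can remove the participant from the potential Hy's Law row and add one to the isolated-ALP row. The first and second of these errors make the safety table look milder than the data.

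**Working it through.** The plan states no figure to reproduce. The check applies the rule to every ordering of dates and then follows the result through Table 2-2.

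**Inputs.** Let *d* be the sample date. SAP 2.7.3 works by calendar date: it matches multi-parameter criteria by the date on which samples were taken.

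- Rule as written: start < *d*, and a stop date exists with stop > *d*.
- Overlap rule for comparison: start ≤ *d*, and either stop ≥ *d* or the record is ongoing.

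| Date pattern | As written | Overlap rule |
|---|---|---|
| start < *d*, stop > *d* | qualifies | qualifies |
| start < *d*, ongoing (no stop) | fails | qualifies |
| start = *d*, stop > *d* | fails | qualifies |
| start = *d*, ongoing (no stop) | fails | qualifies |
| start < *d*, stop = *d* | fails | qualifies |
| start = stop = *d* | fails | qualifies |
| stop < *d* | fails | fails |
| start > *d* | fails | fails |

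The condition is present on the sample day in the first six patterns. The rule as written accepts 1 of 6, and the overlap rule accepts 6 of 6. Both reject the two patterns with no overlap.

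**Example 1 (assumed values).** ALT is 4 × ULN with normal baseline ALT. Nausea began before the sample and still has no stop date at the cut-off.

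- As written: symptoms are not recognised, so the event falls in the row without symptoms.
- Overlap rule: the event falls in the row with symptoms.

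**Example 2 (assumed values).** Bone disease with no stop date; ALT 4, TBL 2.5 and ALP 2.5, all × ULN.

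- As written: bone pathology is not recognised, so the ALP limit is 2. Since 2.5 > 2, the Hy's Law criterion is not met and the isolated-ALP criterion is met.
- Overlap rule: the ALP limit is 3. Since 2.5 ≤ 3, the Hy's Law criterion is met and the isolated-ALP criterion is not.

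**Where it can matter.** The symptom test changes a row only for ALT >3 to ≤5 × ULN, or the corresponding criterion when baseline ALT is raised. The bone-pathology test changes a row only for ALP >2 to ≤3 × ULN: at or below 2 both limits are respected, and above 3 both are exceeded. Gilbert syndrome is named in the footnote and in Table 2-3 but enters no Table 2-2 criterion, so failing the rule moves nobody.

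**Size per participant.** 1/40 = 0.025, or 2.5 percentage points of a row, with the planned sample of about 40.

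**The case against.** The strongest reply is that the exclusion is inferred. Footnote a does not say that a record without a stop date fails, and SAP 5.1.1.1 says only that no end date is invented for an ongoing AE. The same SAP leaves ongoing concomitant-medication end dates unimputed (5.1.2.1), yet Section 2.4.2 counts medications continuing after the start of study drug as concomitant. A programmer could well treat a missing stop date as open-ended. That is a fair analogy, but it covers medications and is not a rule for Table 2-2. It also does nothing for records that start or end on the sample date. Table 2-3 and the eCRS are cited for choosing terms, not for timing.

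The limits on consequence stand. Protocol 10.1.1 has AEs followed to resolution or until judged permanent, so a transient symptom will normally acquire a stop date and, if it spans the sample date, qualify. Investigators act on protocol Table 16-1, which has no such date condition. SAP 2.7.1 lists all AEs, and 2.7.3 lists laboratory abnormalities by participant and visit where normal ranges exist, so a reader can match an elevation with a symptom by hand.

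A reader might infer that ongoing conditions or same-day symptoms can never qualify. The documents do not support that. A condition ongoing at the sample qualifies once it has a later stop date, and so does a symptom that began before the sample date and ended after it. What fails is a record with no stop date at the cut-off, or one whose start or stop equals the sample date.

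**Conclusion.** The rule is wrong as written, and the point is minor. Followed literally, footnote a excludes records that show the condition present at the sample, and Table 2-2 can then place a participant in the wrong row. This is a stated rule that gives a wrong result, not merely a missing detail.

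The conclusion rests on reading the two date conditions as strict and on ongoing medical history carrying no stop date. The SAP says nothing to the contrary on either. How many participants would be misplaced cannot be computed, because the documents give no frequency for the combinations required; the 2.5 points is a unit, not an estimate. The effect is confined to a descriptive safety table and touches no efficacy result or decision threshold.

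**What to change.** Replace the timing clause of footnote a with: *start date on or before the date of the laboratory sample, and either stop date on or after that date or the record is flagged as ongoing*. Apply it to AEs and medical history alike.

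Do not treat an unknown stop date as ongoing. SAP 5.1.1.1 names a missing end year and an ongoing event as separate cases, and a resolved bone disorder with an unknown end would otherwise count as present indefinitely. Give such records their own stated rule, for example listing them for review.

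The cost is about a sentence or two in the SAP and a small change to the derivation, with no new data. The downside is that slightly more events will be classed as symptomatic. Some participants with bone disease will leave the isolated-ALP row and, where the ALT/AST and bilirubin criteria are also met, enter the potential Hy's Law row.

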2.7.3.1 Electrocardiogram (ECG)

The following ECG parameters will be obtained during the study and summarized descriptively: ECG mean heart rate, RR interval, PR interval, QRS duration, QT interval and corrected QT interval by the Fridericia criteria (QTcF). Summary statistics (absolute values and change from baseline) for all ECG parameters will be provided by time point; the number of participants with values outside the normal range will be displayed. Where normal ranges are available, participants with abnormalities in ECG data will be listed by visit/time.

Categorical summary statistics for ECG alert values will also be provided based on the number and proportion of participants meeting or exceeding the following predefined limits any time post baseline:

- QRS > 120 ms
- QRS increase from baseline > 25%
- QTcF > 500 ms
- QTcF increase from baseline > 60 ms
- Resting heart rate sinus rhythm (HR) < 30 bpm
- HR decrease from baseline \geq 25%
- HR > 130 bpm

In addition, a listing of these participants will be produced. A listing of all newly occurring or worsening abnormalities will be provided.

Noticeable ECG abnormalities such as ventricular tachycardia, new complete heart block (Grade III AV block) and Mobitz II AV block are reported as AEs and will be described as part of AEs.

When ECG is performed in triplicate at each visit, the average between the 3 values must be used for summaries and before identification of the abnormalities listed above.

2.7.3.2 Vital signs

Vital signs measurements include systolic blood pressure (SBP) and diastolic blood pressure (DBP), pulse rate, body temperature, height and body weight. Summary statistics (absolute on-treatment values and change from baseline) will be provided for all vital signs data (weight, temperature, pulse rate, SBP, DBP) by visit/time. On-treatment values will be defined as in [Section 2.7](#).

Where ranges are available, abnormalities will be summarized and listed by participant and visit/time. Arithmetic mean (SD) of absolute values over time for SBP, DBP and pulse rate will also be provided.

Frequency tables displaying the number of patients with abnormal blood pressure or heart rate values (by visit or worst post baseline) can be displayed.

Boundaries are the following:

- Blood pressure (BP):
 1. Systolic BP: 100 – 140 mmHg

[figure not shown]
2. Diastolic BP: 65 – 95 mmHg

- Heart rate:
 1. ≤ 50 bpm
 2. ≥ 120 bpm
- Temperature > 38.3 °C (>101 °F)

2.10 Patient-reported outcomes

In this study, the question addressed by the analysis of PRO measurements is whether treatment with iptacopan improves patient-reported fatigue symptoms as measured by the FACIT-Fatigue.

[REDACTED]

Changes in scores of fatigue using the FACIT-Fatigue questionnaire are a secondary endpoint and the analysis is described in [Section 2.6](#).

[figure not shown]
[REDACTED]

All supportive analyses of the performance of the FACIT-Fatigue questionnaire (including responder analyses derived from a priori definition of a meaningful change) and of the behavior of meaningful change over time as well as of the impact of clinical endpoints as reflected in the FACIT-Fatigue will be detailed in a separate analysis plan for PROs.

[REDACTED]

[REDACTED]

[REDACTED]

2.13 Interim analysis

No formal interim analyses of efficacy are planned in this study. A data cut-off will be applied and a clinical study report (CSR) will be produced for submission at the time the last patient has completed the core treatment period. An additional CSR will be produced when the last participant has completed the last visit in the extension treatment period, when the final study database has been locked. In addition, if deemed required (e.g. to support regulatory submissions to Health Authorities) interim safety analyses may be produced while the study is still ongoing. If there is an interim lock for safety analyses, [REDACTED]

[REDACTED] The interim report will not consider inferences based on efficacy.

Safety data will be monitored by an independent DMC, and analyses to the effect of this evaluation will be performed during the course of the study with the frequency to be determined in the DMC Charter. Access to a limited number of efficacy measurements by the DMC will be

provided solely for the purpose of evaluating benefit of treatment with iptacopan against any risk. The DMC will function under the the DMC Charter which has been finalized. The Charter includes guidelines for communication concerning safety of participants between the DMC and the sponsor representative to ensure that these are in keeping with the sensitive nature of the open label trial and do not introduce bias.

3 Sample size calculation

The sample size is calculated based on the half-width (the margin of error in the estimate) of a 2-sided 95% confidence interval for the proportion of participants reaching the status of responder (primary endpoint). The proposed sample size of 40 participants is sufficient to achieve a target absolute margin of error not larger than 0.155.

The different scenarios of observed response rate and its 95% confidence intervals are shown in [Table 3-1](#).

Table 3-1 Precision of response rate with N = 40

Sample Size	Observed Response Rate	Unadjusted 95% Confidence Interval
40	30%	(15.8%,44.2%)
40	40%	(24.8%,55.2%)
40	50%	(34.5%, 65.5%)
40	60%	(44.8%,75.2%)

The lower bound of the two-sided 95% confidence interval of the response rate obtained from the primary analysis will be compared to a threshold of 15% and exceeding the threshold is sufficient for demonstration that iptacopan improves hematological response in PNH patients with hemolysis and anemia in the absence of transfusions.

For the sample size of 40 participants, given the observed proportion of responders is 40%, there is 96.4% probability that the lower bound of the 2-sided 95% CI will exclude a threshold of 15%.

4 Change to protocol specified analyses

The “indicator of transfusion dependence” is defined to be “prior to starting study treatment” instead of “at enrollment” (defined in study protocol Section 12.4.2).

5 Appendix

